TEG is limited, however, by the requirement that the analysis be performed within minutes of blood draw to prevent clot formation unless the addition of citrate occurs.³⁷ It has been demonstrated the TEG can assess coagulopathy, platelet dysfunction and most importantly, hyperfibrinolysis at an early stage following injury and is the most rapid available test for providing reliable information on coagulopathy in significantly injured patients.^{38,39} If not more important, the technology has been deemed feasible for use in a deployed military setting as well as for civilian use.⁴⁰

C.5. Early tranexamic acid reduces mortality post-injury:

In a large, civilian, multicenter, randomized, controlled trial (CRASH-2 trial) on the use of tranexamic acid in patients at risk of bleeding, a significant reduction in mortality was found with its use.⁴¹ Tranexamic acid is a lysine analog that is known to interfere with binding sites on plasminogen and inhibit fibrinolysis.⁴² Inclusion criteria for the trial included hypotension SBP <90 mm Hg or tachycardia (> 110 beats per min), in patients at risk of significant hemorrhage within 8 hours from injury. Dosing of tranexamic acid was given in a bolus 1 gram dose over approximately 10 minutes followed by an infusion dose (additional 1 gram) over eight hours. This therapy was subsequently found in exploratory analysis to be beneficial in those who received tranexamic acid in the first 3 hours from injury and strongest in those patients who received it in the first hour following injury.⁴³ Pre-specified analysis of the trial data demonstrated that the mortality benefit attributable to tranexamic

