H.3.1. Prehospital Phase Intervention: Once inclusion and exclusion are verified while the patient is being transported via emergency medical transport to a STAAMP trial participating center, in a randomized, double blinded fashion, either 1 gram bolus of tranexamic acid diluted in 100cc of normal saline (pre-prepared on emergency vehicle) or placebo of identical volume will be infused intravenously or intraosseously (if IO access was obtained due to a clinical need per standard of care) into the patient over approximately 10 minutes (“Bag A”). After receiving the prehospital phase intervention, standard operating procedures utilizing goal directed crystalloid infusion will be followed (see **H.7. Prehospital Standard Operating Procedures** below)

H.3.2. In-hospital Phase Intervention: Upon arrival, patient blood and labs will be sampled and arrival rapid-TEG analysis will be performed within first 6 hours. After inclusion and exclusion criteria verification by research staff, in a double blinded, randomized fashion, those patients who received tranexamic acid in the prehospital phase will receive 1 of 3 different dosage regimens:

1. Standard Tranexamic acid Dosing: 1 gram infusion over approximately 8 hours
2. Repeat Tranexamic acid Dosing: 1 gram bolus **and** 1 gram infusion over approximately 8 hours
3. Abbreviated Tranexamic acid Dosing: No further tranexamic acid to be given

For intervention blinding purposes, each patient will receive both a bolus dose (either tranexamic acid or placebo), “Bag B,” and 8 hour infusion (either tranexamic acid or placebo), “Bag C,” depending on the randomized dosing regimen. (Figure 13. below)

H.3.2.1 Adjustment For Renal Insufficiency: Subjects with a known or suspected history of renal insufficiency will receive a renal dose adjustment for the 8 hour repeat infusion (Bag C). The Estimated Body Weight Table will be used to determine the dose (Figure 12). The dose will be capped at 1000 mg.

1. Standard Dosing: bolus- no dose adjustment / infusion- 1.25 mg/kg/hr x 8hrs
2. Repeat Dosing: bolus- no dose adjustment / infusion- 1.25 mg/kg/hr x 8hrs
3. Abbreviated Dosing: bolus- no dose adjustment / infusion- 1.25 mg/kg/hr x 8hrs

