I.2 Secondary Clinical Outcomes: Secondary clinical outcomes will include the incidence of hyperfibrinolysis (EPL > 7.5% by rapid-TEG analysis) upon arrival to the trauma bay within the first 6 hours, the incidence of acute traumatic coagulopathy (INR > 1.4), 24 hour mortality, acute lung injury, multiple organ failure, the development of nosocomial infection, early (24hr) seizures, in-hospital pulmonary embolism, presenting base deficit, 24 hour crystalloid requirements and 6 hour and 24 hour blood and blood component transfusion requirements (PRBC, FFP and platelets). *These same clinical outcomes will similarly be used for the randomized tranexamic acid dosage regimen comparison.*

I.3. Secondary Laboratory/Mechanistic Outcomes: All laboratory/mechanistic outcomes will be measured during the first 6 hours from trauma center arrival and at 12 and 24 hours (+/- 12 hours) out from injury. Those laboratory/mechanistic outcomes including flow cytometry which require fresh blood samples will be performed only at the University of Pittsburgh on a subset of patient samples unless participating centers have specific capabilities and following appropriate training for standardization. *These same laboratory/mechanistic outcomes will similarly be used for the randomized tranexamic acid dosage regimen comparison at 12 and 24 hours post-injury.*

I.4. Clinical Outcomes Methods/Definitions: All clinical outcomes will be prospectively evaluated for throughout ICU and hospital admission and the timing from the day of initial injury will be recorded for time-to-event statistical analysis.

I.4.1. 30 day and 24 hour mortality: 30 day mortality will be prospectively recorded from the day of trauma bay arrival. Over the first 24 hours we will document and record the time of death in hours. We suspect that patients enrolled will have a significant percentage of mortality that occurs in the first 24hrs.

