I.5. Laboratory/Mechanistic Outcome Methods/Definitions: All measurements will be performed within 6 hours of arrival and at 12 and 24 hours post injury (+/- 12 hours) for the randomized dosage regimen comparison. One more additional blood sample will be collected at 72 hours (\pm 12 hrs) for D-dimer, activated Protein C levels and plasmin-antiplasmin complexes measurements. Excluding r-TEG analysis and PT/ INR measurements, all blood and serum samples will be spun, stored and batched at their respective institution and delivered to the University of Pittsburgh where formal ELISA immunoassay measurements will be undertaken. Those laboratory/mechanistic outcomes including flow cytometry which require fresh blood samples will be performed only at the University of Pittsburgh on a subset of patient samples unless participating centers have specific capabilities and following appropriate training for standardization.

I.5.1. Coagulopathy and TEG parameters (Aim#2): To appropriately characterize differences in coagulopathy between tranexamic acid and placebo, in addition to r-TEG measurements of hyperfibrinolysis, presenting PT/ INR and additional TEG parameters will also be measured (ACT, r-value, k-time, α -angle, maximal amplitude, and G-values). All rapid TEG measurements will be performed within 6 hours of arrival and at 12 and 24 (+/- 12 hours) hours post injury. TEG analysis will be performed on a TEG[®] 5000 Thromboelastograph[®] Hemostasis Analyzer which will reside within the emergency department of each participating site. Standard laboratory INR will be drawn and measured at each institution within 6 hours of arrival and at 12 and 24 hours (+/- 12 hours). To further quantify the coagulopathy and hyperfibrinolysis post injury in these patients, D-dimer, activated Protein C levels and plasmin-antiplasmin complexes will be measured by ELISA plate assay. (ANIARA, USCN Life Science Inc., DRG International, Inc.) Plasmin-antiplasmin complexes may represent a more common, subclinical measurement of fibrinolytic activity that is not able to be assessed using standard TEG analysis, but elevated levels are associated with significantly worse outcome post injury and may be a marker than demonstrates the mechanism by which tranexamic acids has it beneficial effects.

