interdepartmental resource with laboratory facilities, an experienced and professionally-trained staff of clinical research coordinators, and 24 hour around the clock screening capabilities. They have extensive experience with data entry, multi-center data coordination, training, IRB liaison needs, web-based data entry platforms and specimen management and storage. MACRO follows a cost center model and provides 'cost-neutral' services to clinical investigators from diverse specialties in order to conduct clinical and translational research. The University of Pittsburgh will be the data and specimen coordinating center for the proposal. MACRO research coordinators and participating site research coordinators will document and verify all trauma arrivals via emergency medical transport for enrollment. Those patients who met inclusion and exclusion criteria en route via emergency medical transport that were enrolled will be verified and enrolled patients will undergo initial laboratory and blood sampling and will have point of care rapid thromboelastography (TEG) performed for coagulation parameter measurements within 6 hours of patient arrival. **All guidelines and requirements for notification for exception of consent for emergency research will be followed.** Patients at risk for hemorrhage during or directly preceding emergency medical transport represents an immediate life threatening condition with the patient commonly intubated, unconscious, or not responsive, it will not be possible to contact legal representatives at the time of study entry. Research coordinators will make every effort to contact legal representatives after admission to the hospital to notify them that the patient was enrolled in a randomized trial. Research personnel will attempt to contact the subject's legally authorized representative as soon as feasible for notification of enrollment and will provide an opportunity to opt out from ongoing participation. Summary of these efforts will be documented in the patient's chart. If the subject becomes competent during the study period then he/she will be approached by research personnel for notification of enrollment and a similar provision of an opportunity to opt out from ongoing participation.

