In-hospital Phase Intervention: Upon arrival, patient blood and labs will be sampled and arrival rapid-TEG analysis will be performed within first 60 minutes. After inclusion and exclusion criteria verification by research staff, in a double blinded, randomized fashion, those patients who received tranexamic acid in the prehospital phase will receive 1 of 3 different dosage regimens:

1. *Standard Tranexamic acid Dosing:* 1 gram infusion over 8 hours

2. *Repeat Tranexamic acid Dosing:* 1 gram bolus and 1 gram infusion over 8 hours
3. *Abbreviated Tranexamic acid Dosing:* No further tranexamic acid to be given

For intervention blinding purposes, each patient will receive both a bolus dose (either tranexamic acid or placebo) and 8 hour infusion (either tranexamic acid or placebo) depending on the randomized dosing regimen.

Placebo/Control Arm: Prehospital phase patients randomized to placebo will receive identical placebo diluted in 100cc of normal saline and infused over 10 minutes. Patients who received prehospital phase placebo will receive in-hospital identical placebo bolus and 8 hour placebo infusion for blinding purposes

Randomization: The randomization scheme will have both a prehospital phase and in-hospital phase.

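### The arrival sample that tests prehospital TXA may be taken up to 6 hours after arrival and need not precede Bag B, so in-hospital TXA can be mixed into the prehospital comparison

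*Combined protocol and SAP*

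**What the plan says.** Secondary Aim 1 and its hypothesis (E.3.1) concern prehospital TXA against placebo. The outcomes are hyperfibrinolysis (estimated percent lysis above 7.5%), INR above 1.4 at presentation, and other presenting coagulation markers.

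The sampling window appears in several places:

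- H.3.2: "Upon arrival, patient blood and labs will be sampled and arrival rapid-TEG analysis will be performed within first 6 hours".
- I.2 defines the hyperfibrinolysis outcome as measured "upon arrival to the trauma bay within the first 6 hours".
- I.3, for all laboratory and mechanistic outcomes: "measured during the first 6 hours from trauma center arrival and at 12 and 24 hours (+/- 12 hours) out from injury".
- I.5.1: "Standard laboratory INR will be drawn and measured at each institution within 6 hours of arrival".
- Section M has the rapid TEG "performed for coagulation parameter measurements within 6 hours of patient arrival".
- The DSMB charter (Appendix 3, In-hospital Phase Intervention) differs: "arrival rapid-TEG analysis will be performed within first 60 minutes".

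On treatment, H.3.2 gives every patient a bolus bag (Bag B) and an 8-hour infusion bag (Bag C). Among patients given prehospital TXA, the standard regimen has active drug in Bag C, the repeat regimen in both bags, and the abbreviated regimen in neither. Under H.4 the prehospital-placebo arm receives placebo in both.

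On analysis, section J groups all enrolled patients by prehospital assignment. J.2 names chi-square tests and parametric or non-parametric comparisons, with no term for draw time or in-hospital regimen.

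**The concern.** The aim is about the state in which patients present after the prehospital bolus. A window of up to 6 hours, with no stated order relative to Bag B, allows that state to be measured after in-hospital study drug has begun. The added exposure is not balanced: only the prehospital-TXA arm can receive active drug in hospital.

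Two distortions are possible, in opposite directions. If in-hospital TXA lowers fibrinolysis, late draws enlarge the apparent prehospital effect. If resuscitation has already corrected INR or TEG in both arms, late draws shrink it. H.2 reports, from the sponsor's own air-transport data, that more than 65% of such patients are transfused within 24 hours, so the second route is not remote.

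At stake is what a result on Secondary Aim 1 means: an effect of the 1 g prehospital dose, or of that dose plus whatever had been given by the time of the draw.

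**Working it through.** The plan states no figure for this point, so there is none to reproduce. The check is of sequence, then of possible size.

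**Sequence.** H.3.2 mentions sampling on arrival and then describes the regimens. Its time limit is attached to the TEG analysis. I.5.1 attaches the limit to the INR draw as well as its measurement. C.4 notes for rapid TEG "the requirement that the analysis be performed within minutes of blood draw to prevent clot formation" unless citrate is added, so without citrate a late analysis implies a late draw. No readable text states when Bag B starts or requires the draw to come first. N.2 and N.3 name neither sample draw times nor bag start times among the data elements.

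**Who is exposed.** 497 per arm (K.1). Three regimens in blocks of 9 (H.5.2); the ratio is not stated and 1:1:1 is assumed. Active drug in either bag: 497 × 2/3 ≈ 331. Active Bag B: 497 / 3 ≈ 166. Placebo arm: 0.

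**Dose by hour 6, the latest permitted draw.** Let Bag B start s hours after arrival (assumed 0.5 to 3) and run 10 minutes (1/6 h), followed by Bag C at 1 g over 8 h. Renal adjustment is ignored.

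- Bag C delivered = (6 − s − 1/6) / 8 g
- Mean in the TXA arm = [repeat (2 + C) + standard (1 + C) + abbreviated 1] / 3

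| s (h) | Bag C (g) | Repeat (g) | Standard (g) | Abbreviated (g) | Mean (g) | In-hospital share |
|---|---|---|---|---|---|---|
| 0.5 | 0.67 | 2.67 | 1.67 | 1.00 | 1.78 | 0.78/1.78 = 44% |
| 3 | 0.35 | 2.35 | 1.35 | 1.00 | 1.57 | 0.57/1.57 = 36% |

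For any draw before Bag B the mean is 1 g and the in-hospital share is 0%.

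**Averaged over the window.** Hour 6 is the extreme. If draws were spread evenly over 0 to 6 h (an assumption that H.3.2's arrival wording does not favour), and ignoring the 10-minute bolus time:

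- TXA-arm draws after active in-hospital drug has started = (2/3) × (6 − s)/6
- Mean TXA = 1 + (2/3) × (6 − s)²/96 + (1/3) × (6 − s)/6

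| s (h) | Exposed draws | Mean TXA (g) |
|---|---|---|
| 0.5 | 61% | 1 + 0.21 + 0.31 = 1.52 |
| 2 | 44% | 1 + 0.11 + 0.22 = 1.33 |
| 3 | 33% | 1 + 0.06 + 0.17 = 1.23 |

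**Illustration of consequence.** Suppose the prehospital dose has no effect, the control hyperfibrinolysis rate is p, in-hospital TXA has relative risk RR on any late draw, and a fraction f of draws is late. The TXA-arm rate is then q = p × [1 − (2/3) × f × (1 − RR)]. For p = 0.20, RR = 0.50 and f = 0.5: q = 0.20 × 0.833 = 0.167, a difference of 0.033. With 497 per arm and two-sided 0.05 (normal approximation), the null standard error is √(2 × 0.1833 × 0.8167 / 497) = 0.0245 and the critical difference is 1.96 × 0.0245 = 0.048. The chance of a significant result is about 0.27.

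Over p = 0.10 to 0.30 and RR = 0.75 to 0.50, all assumed:

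| Late draws f | Chance of a significant prehospital result |
|---|---|
| 0 | 0.05 |
| 0.25 | 0.06 to 0.14 |
| 0.5 | 0.07 to 0.42 |
| 1 | 0.15 to 0.96 |

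**The case against.** The best case for the plan is that it already intends an early draw. H.3.2 has blood sampled on arrival, before it describes the regimens. Bag B can follow only after eligibility is verified, the web allocation is obtained and cross-checked, and the pharmacy has prepared the bags (H.5.2). E.3.1 speaks of presenting and arrival values. C.4 allows for citrate, and the documents do not say whether the trial's rapid TEG uses it, so a 6-hour analysis limit need not mean a 6-hour draw limit. Figure 13, the two-phase schematic, was not available for this check and may show an order. J.2 generally intends confidence limits for secondary outcomes, which lowers the weight of any single test.

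Much of this stands. Late draws are permitted, not shown to happen, and the plan's likely intention is a sample close to arrival. It does not remove the point: the INR draw itself has a 6-hour window in I.5.1, I.2 builds the window into the outcome definition, and the charter's 60 minutes shows that the limit is unsettled.

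A reader might infer that most arrival samples would be contaminated. With even draws and Bag B starting at 0.5 to 2 h, (6 − s)/6 gives 92% to 67% of draws after Bag B. That counts placebo bags and rests on a draw pattern the documents do not give. On the same assumptions, draws after active drug has started are 61% to 44% of the TXA arm.

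A reader might also infer that Aim 4 loses its baseline. Hypotheses 4A to 4D and J.3 compare the randomised regimens directly, and no text uses the arrival sample as a pre-regimen baseline.

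**Conclusion.** The concern holds as a defect in the definition of the arrival sample. Following the window as written can produce a prehospital comparison on hyperfibrinolysis, INR and the other presenting markers that includes in-hospital TXA in one arm only, with no analysis planned to separate the two. The extent is unknown. The hour-6 mean of about 1.6 to 1.8 g is an upper case resting on 1:1:1 allocation and a Bag B start of 0.5 to 3 h; draws before Bag B carry no such excess. The net direction is also unknown, since early transfusion can act the other way.

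Two stronger inferences are not supported. One is that in-hospital treatment would answer the aim in place of the prehospital dose. All patients in the TXA arm are assigned that dose and about a third receive no further drug, so late draws blend effects; they do not substitute one for the other. The other is that attribution is lost. The abbreviated regimen against placebo is a randomised contrast with no in-hospital TXA on either side, whatever the draw time. Randomisation also remains valid for the whole TXA strategy. The primary outcome of 30-day mortality does not use this sample.

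**What to change.** - **Definition.** In H.3.2, I.2, I.3, I.5 and M, define the arrival research sample as the one drawn before Bag B starts, and state draw time and analysis time separately. This defines a measurement and takes no position on when Bag B is given.
- **Consistency.** Reconcile the protocol's 6 hours with the charter's 60 minutes.
- **Data.** Record the draw time and the start times of Bag B and Bag C.
- **Analysis.** In J.2, keep the intention-to-treat comparison of all arrival samples as the main one. Prespecify two sensitivity analyses: (a) abbreviated regimen versus placebo, among patients who reached in-hospital allocation; (b) draws before Bag B only, with a statement that this selects on an event after randomisation, since late draws may cluster in the sickest patients.
- **Check for (a).** H.3.2.1 lists a renally adjusted infusion rate under the abbreviated regimen, while H.3.2 gives that regimen no further TXA. These passages must be reconciled so that (a) is clearly free of in-hospital drug.

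The cost is protocol and laboratory-manual wording plus three time stamps, with no added draws or visits. The downsides are that some samples will fall outside the arrival definition, and that (a) uses only about one third of the TXA arm (about 166 of 497) and so is less precise.

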Secondary Hypothesis 3B: Prehospital tranexamic acid as compared to placebo will attenuate trauma-induced pro-inflammatory changes and immunosuppression by reducing the early inflammatory cytokine response (GM-CSF, IFN- γ , IL-1 β , IL-2, IL-4, IL-5, IL-6, IL-8, IL-10 and TNF- α), HMGB1 levels and early inflammatory gene responses as measured by RT-PCR.

E.3.4. Secondary Aim#4: Determine whether different dosing regimens of tranexamic acid upon arrival in the hospital are associated with improvements in hyperfibrinolysis, markers of coagulopathy, clinical outcomes, platelet and leukocyte activation and the early inflammatory response.

Secondary Hypothesis 4A: Repeat dosing of 1 gram of tranexamic acid followed by 1 gram over approximately 8 hours after hospital arrival in patients who have already received 1 gram of prehospital tranexamic acid will lower the incidence of 12 hour (from arrival) hyperfibrinolysis (estimated percent lysis > 7.5%), coagulopathy (INR > 1.4) and improve r-TEG markers of coagulopathy, D-dimer levels, activated protein C levels and plasmin-antiplasmin complex levels as compared to standard dosing of tranexamic acid (1 gram over approximately 8 hours) or abbreviated dosing (no additional tranexamic acid).

Secondary Hypothesis 4B: Repeat dosing of 1 gram of tranexamic acid followed by 1 gram over approximately 8 hours after hospital arrival in patients who already received prehospital tranexamic acid will lower the incidence of 24 hour and 30 day mortality, acute lung injury, multiple organ failure and nosocomial infection as compared to standard dosing or abbreviated dosing.

Secondary Hypothesis 4C: Repeat dosing of 1 gram of tranexamic acid followed by 1 gram over approximately 8 hours after hospital arrival in patients who already received prehospital tranexamic acid will reduce 12 hour (from arrival) base deficit, 24 hour crystalloid requirements and 6 hour and 24 hour blood and blood component transfusion requirements (PRBC, FFP and platelets) as compared to standard dosing or abbreviated dosing.

Secondary Hypothesis 4D: Repeat dosing of 1 gram of tranexamic acid followed by 1 gram over approximately 8 hours after hospital arrival in patients who already received prehospital tranexamic acid will reduce 12 hour and 24 hour (from arrival) markers for platelet and leukocyte activation, plasmin

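### The renal-adjustment list gives the abbreviated arm an 8-hour infusion expressed as a drug dose, although that arm is defined as receiving no further tranexamic acid; whether its Bag C holds drug or placebo is not stated

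*Combined protocol and SAP*

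**What the plan says.** H.3.2 sets out three in-hospital regimens for patients who received tranexamic acid before arrival. The third is "Abbreviated Tranexamic acid Dosing: No further tranexamic acid to be given". Secondary Hypothesis 4A (E.3.4) describes it the same way, as "abbreviated dosing (no additional tranexamic acid"), and the DSMB charter (Appendix 3, In-hospital Phase Intervention) repeats the definition.

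H.3.2 also says that, to keep the blind, each patient receives both a bolus bag (Bag B) and an "8 hour infusion (either tranexamic acid or placebo), “Bag C,” depending on the randomized dosing regimen".

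H.3.2.1 then deals with patients whose renal insufficiency is known or suspected. They "will receive a renal dose adjustment for the 8 hour repeat infusion (Bag C"), and "The dose will be capped at 1000 mg". The section has one line per regimen:

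- "Standard Dosing: bolus- no dose adjustment / infusion- 1.25 mg/kg/hr x 8hrs"
- "Repeat Dosing: bolus- no dose adjustment / infusion- 1.25 mg/kg/hr x 8hrs"
- "Abbreviated Dosing: bolus- no dose adjustment / infusion- 1.25 mg/kg/hr x 8hrs"

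Apart from the regimen name, the three lines are identical. The section bases the adjustment on the tranexamic acid package insert. Its weight table (Figure 12, dose adjustment) converts the rate into mg and into a volume to draw from the vial.

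**The concern.** One subsection attaches a weight-based infusion to an arm that its parent section defines as getting no drug in hospital. H.3.2.1 does not use the word placebo. A rate in mg/kg/hr, a cap in mg and a vial volume are how one writes an instruction to prepare active drug.

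The text is used by the investigational drug service and the site pharmacies, which prepare the in-hospital treatment (H.5.2). H.1 names four sites and one alternate, so sites could read it differently.

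Two things are at stake. The first is whether a patient with impaired renal function who was assigned no further drug is given some. The second is the dosing comparison in Aim 4, because in these patients the standard and abbreviated regimens would become the same treatment.

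**Working it through.** **Inputs.** Rate 1.25 mg/kg/hr for 8 hours, cap 1000 mg (H.3.2.1). Weight-band doses (Figure 12). Prehospital bolus 1 g = 1000 mg (H.3.1). Abbreviated arm: 0 mg further drug in hospital (H.3.2, Hypothesis 4A, DSMB charter).

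**Step 1: reproduce the plan's own table.** Dose per kg = 1.25 × 8 = 10 mg/kg. Multiplying by the lower limit of each weight band and capping at 1000 mg gives:

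| Band (kg) | 10 mg/kg × lower limit (mg) | Figure 12 (mg) |
|---|---|---|
| 20-29.9 | 200 | 200 |
| 30-39.9 | 300 | 300 |
| 40-49.9 | 400 | 400 |
| 50-59.9 | 500 | 500 |
| 60-69.9 | 600 | 600 |
| 70-79.9 | 700 | 700 |
| 80-89.9 | 800 | 800 |
| 90-99.9 | 900 | 900 |
| >100 | 1000 | 1000 |

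All nine rows agree. The table is therefore the listed rate turned into doses, and the rate on the abbreviated line leads to the same mg figures as the other two.

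**Step 2: total tranexamic acid under each reading, 70-79.9 kg band, renal rule applied.**

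| Regimen | Prehospital + Bag B + Bag C (mg) | Total (mg) |
|---|---|---|
| Abbreviated, as defined in H.3.2 | 1000 + 0 + 0 | 1000 |
| Abbreviated, H.3.2.1 read literally | 1000 + 0 + 700 | 1700 |
| Standard | 1000 + 0 + 700 | 1700 |
| Repeat | 1000 + 1000 + 700 | 2700 |

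Under the literal reading the abbreviated total equals the standard total. This holds in every band: each is 1000 mg plus the table dose, so 1200 to 2000 mg across the table. The lowest bands are unlikely to matter in a trial that excludes patients under 18.

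**Step 3: how many patients.** The documents do not say how many patients have known or suspected renal insufficiency. If the 497 patients in the tranexamic acid group were split equally over the three regimens, the abbreviated arm would hold 497 / 3 ≈ 166. Only the renal patients among those would be affected.

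**Step 4: test the alternative reading against the text.** The standard and abbreviated lines also carry a bolus entry, although H.3.2 gives neither arm an active in-hospital bolus. For those two arms the bolus entry can only describe a placebo Bag B. At least part of the list is therefore written by bag and not by active drug, and the infusion entry on the abbreviated line can be read the same way. Nothing in H.3.2.1 says that it must be.

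**The case against.** The strongest reply is that there is no real conflict. The sentence just before H.3.2.1 makes Bag C drug or placebo by regimen, and the synopsis says that placebo bags are used for blinding in all arms. With the arm defined as receiving no further drug, its Bag C can only be placebo. The bolus entries point the same way. H.3.2.1 presents itself as an adjustment and does not claim to redefine the arms. The pharmacies are unblinded, hold the allocation and check it with research staff (H.5.2), so they would have to override the arm definition to give drug. A vial volume does not settle the matter either, because H.3 says that placebo is supplied as well as tranexamic acid. The two-phase schematic (Figure 13) is not reproduced in the text available to me and may show the bag contents by arm.

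Most of this stands, and it makes the blinding reading the likely intent. It does not remove the point: the reader must infer from other text that a rate written as a drug dose means placebo on one line and drug on the other two.

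A reader might infer more than the documents support:

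- **That the protocol orders active drug for the abbreviated arm, or that patients were misdosed.** The Bag C sentence and the bolus entries tell against the first, and nothing in the documents shows the second.
- **That leaving the placebo arm off the list proves the list means active drug.** H.3.2.1 sits under the interventional-arm section and controls have their own section, H.4, so the silence is weak evidence. It does leave a smaller gap: H.4 has no renal rule, so how the control arm's Bag C is matched is unstated.

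**Conclusion.** The inconsistency is real and lies in the current text. H.3.2, Hypothesis 4A and the DSMB charter give the abbreviated arm no further drug, while H.3.2.1 lists an infusion for it in the terms of a drug dose and does not mark it as placebo.

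If followed literally, the difference is 10 mg/kg against none. That harm depends on a pharmacy taking the line at face value. It is confined to a renal subgroup whose size is not given, and it touches only the dosing comparison in Aim 4. The primary comparison is by prehospital assignment, so the primary analysis and the sample size of 994 are not materially affected.

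I rate it a moderate clarification of a pharmacy instruction. A reader might take it for a defect that undermines the trial, but the conditional harm and the surrounding blinding text do not support that. The conclusion assumes that Figure 13 does not already settle the contents of Bag C; if it does, the point reduces to bringing H.3.2.1 into line with the figure.

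**What to change.** Reconcile H.3.2, H.3.2.1, H.4 and Secondary Hypothesis 4A. On each renal-adjustment line, and for the placebo arm, state whether Bag C contains tranexamic acid or placebo when the renal rule applies. If an entry is there only to match bags for blinding, say so in H.3.2.1 itself. Which content is intended is for the sponsor to state; this review proposes no dose.

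The cost is a few lines of protocol text and the same change in any pharmacy preparation instructions. It needs no change to the sample size, the randomization or the primary analysis.
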